7.1 Study Population

7.1.1 Composition of cohort

The cohort will consist of three groups of subjects (Table 2): Group A, HIV seropositive subjects who have ≥ 400 CD-4 cells and no

clinical manifestations of HIV infection; Group B, HIV seropositive subjects with < 400 CD-4 cells and/or clinical manifestations of HIV infection; and Group C, HIV seronegative homosexual/bisexual men and intravenous drug users.

Each Clinical Center will recruit a study population that is approximately representative of the HIV transmission categories in their locales. The categories include homosexual/bisexual men, intravenous drug users, and seropositive women who have no risk factors other than sexual contact with presumed HIV infected men. For purposes of analysis, each transmission category will be examined separately.

Target quotas have been established for the study as a whole and for each Clinical Center. Table 3 shows the transmission category quotas for each of the eight centers. The apportioning of subjects among the three groups (A, B, C) and transmission categories will be monitored by the Coordinating Center, and the Clinical Centers will be guided in recruitment to reach their quotas. Because the study is not intended to be population-based, no attempt is made to enroll a truly representative group or a predetermined number of consecutive subjects.

Table 3
Target Quotas for HIV Transmission Categories by Center

	H/B(1)	IVDU(2)	Partners(3)	Total
New York	130	60	10	200
Newark	0	190	10	200
Detroit	140	40	20	200
Chicago	180	10	10	200
San Francisco	170	20	10	200
Los Angeles	180	10	10	200
Frankfurt	150	40	10	200
	950	370	80	1400

(1) H/B = Homosexual/Bisexual men

(2) IVDU = Intravenous drug user

(3) Partners = Seropositive female sexual partners of HIV infected men

7.1.2 Inclusion criteria

- 1) Membership in an HIV transmission category: homosexual/bisexual men, intravenous drug users, seropositive female partners of presumed HIV infected men.
- 2) Willing to have HIV antibody status determined.
- 3) Willing to have evaluations for symptoms or findings suggestive of pulmonary disease performed in one of the Clinical Centers.
- 4) Willing and able to provide informed consent.
- 5) Willing to be informed of HIV antibody status as required by Federal regulations.

7.1.3 Exclusion criteria

- 1) Younger than 18 years
- 2) Presence of a nonHIV-related process likely to affect survival
- 3) Judged unwilling or unable to cooperate with the study protocol
- 4) Use of immunosuppressive therapy (Table 4) within the past six months
- 5) Presence of an underlying disorder that makes future use of immunosuppressive therapy likely
- 6) Lung disease that may interfere with evaluations (Table 4)
- 7) Presence of pulmonary symptoms at baseline evaluation (Table 4) either new symptoms or a worsening of chronic symptoms
- 8) Current or previous AIDS-defining diseases (Subjects who meet all inclusion criteria and have no exclusion criteria yet have an AIDS-defining disease diagnosed on the initial evaluation will not be excluded.) (Table 4)
- 9) (Applies only to female partners of HIV infected men)
Receipt of blood or blood products or intravenous drug use in past 10 years

NonHIV-related processes likely to interfere with four-year survival include incurable neoplastic diseases, and severe cardiac, liver and renal disease. Such illnesses not only reduce the likelihood that the patient will complete the study, they also represent Table 4

Excluding Conditions and Therapies

1. Immunosuppressive therapy within previous 6 months.
Corticosteroids (systemic administration of >15 mg prednisone or equivalent amount of other preparation for >14 days)
Cytotoxic agents
Antimetabolites Cyclosporin
2. Lung diseases that may interfere with evaluation
Pneumonia, any cause, within 3 months
Invasive pulmonary fungal infection diagnosed within the past 12 months or continuing to receive treatment for such infection
Pulmonary mycobacterial disease diagnosed within the past 12 months or continuing to receive therapy for the disease
Diagnosed diffuse fiberoptic lung disease or sarcoidosis.
3. Respiratory symptoms
Unexplained cough that persists for more than five days
Unexplained breathlessness progressive over \geq five days or severe \geq one day
4. AIDS-defining diseases (MMWR 1987;37:45) (Appendix 10)
Items 1-12 Section I-B CDC definition
Items 1-12 Section II-A CDC definition
Items 1-7 Section II-B CDC definition

Note: Potential study subjects who at the time of initial evaluation are excluded because of any of the exclusions listed above (1-3), except fibrotic lung disease or sarcoidosis may be reevaluated for study entry after an appropriate time interval.

considerable confounding factors in the interpretation of diagnostic studies and natural history data.

Circumstances decreasing the likelihood or capability to adhere to the protocol include the presence of advanced dementia or active psychosis, past history of poor compliance with medical regimens, recent criminal behavior, and plans to relocate during the study period.

The administration of immunosuppressive therapy, including systemic corticosteroids, antimetabolites, cytotoxic agents, and radiation therapy would cause unacceptable confounding of the results because of their potential for direct pulmonary toxicity and their predisposing towards pulmonary infection.

Inclusion of individuals with current or previous AIDS-defining diseases would greatly diminish the study's ability to characterize the early natural history of pulmonary complications. It is anticipated that sufficient numbers of subjects will develop pulmonary complications during the course of the study that the later stages of the natural history can be evaluated adequately.

The presence of current lung diseases would confound the interpretation of many of the evaluations designed to determine if HIV-associated lung disease is present.

7.1.4 Sample size

The determination of sample size was based on: 1) guidelines initially provided in the RFP regarding the total number of subjects to be studied; 2) estimated rates of drop-outs; and 3) the precision that can be achieved in making estimates of key data desired for the study. Each of the 7 Clinical Centers will enroll at least 200 subjects during the first year of the study. All subjects who meet the definition of drop-out within the first 12 months of enrollment will be replaced, hence, the study population will total 1,400 at the end of month 21. Table 5A shows the expected numbers of subjects to be enrolled in the 1st year for the entire study by clinical subgroup and transmission category.

Table 5A
NUMBER OF STUDY SUBJECTS BY CLINICAL STATUS AND
TRANSMISSION CATEGORY TO BE RECRUITED

	A	B	C	Total
H/B(1)	405	405	140	950
IVDU(2)	155	155	60	370
Partners(3)	40	40	0	80
Total	600	600	200	1400

- (1) H/B - Homosexual/Bisexual males
- (2) IVDU - Intravenous Drug Users
- (3) Partners - Seropositive female sexual partners of HIV infected men

The distribution of subjects entered into the study will be monitored by the Coordinating Center with quotas fixed for the subjects in the two HIV seropositive groups and the seronegative group. These relative proportions will be the same for each Clinical Center. The number of subjects from each transmission category will also be monitored by the Coordinating Center and reported periodically to the Clinical Centers. The proportion of patients in each transmission category for the entire study is based on a compilation of estimates for the relative proportion of subjects to be recruited at each Center as shown in Table 3.

The target quotas by study group for each Clinical Center are Group A-85, Group B-85, Group C-30.

Rates of lost to follow-up from several cohorts of HIV seropositive intravenous drug users and gay men have ranged from approximately 12% to 20%. Because most losses are expected to occur in the first year (and these will be replaced), it is anticipated that a total of 1,231 patients will be maintained in the cohort (lost to follow-up rate = 12%). The sample size/precision calculations were based on a total sample size of 1,231. Table 5B shows the anticipated numbers remaining for analysis at completion of the study.

Table 5B
NUMBER OF STUDY SUBJECTS BY CLINICAL STATUS AND
TRANSMISSION CATEGORY TO BE ANALYZED

	A	B	C	
H/B	356	356	124	836
IVDU	136	136	53	325
Partners	35	35	0	70
Total	527	527	177	1231

The relative numbers of patients to be recruited in each of the clinical subgroups was adjusted in order to obtain reasonable precision estimates for several questions listed in Appendix 1.

In designing the sample, it has been assumed that a sufficient number of subjects from Groups A and B will go on to develop pulmonary complications. Data from Moss et al (Ref 5, Section 3) indicate that approximately 5% of asymptomatic HIV seropositive persons with > 400 CD-4 cells will develop an AIDS diagnosis in each year of observation. In nearly all instances (at least recently) the AIDS-defining diagnosis was P. carinii pneumonia. In patients with findings indicative of more severe immunosuppression, the annual incidence of an AIDS diagnosis (again usually P. carinii pneumonia) was 20%. The incidence of other HIV associated pulmonary processes has not been well quantified, thus there are not sufficient data upon which to base sample size calculations.

The sample size of the study is adequate to estimate the prevalence rates of major pulmonary complications (i.e., P. carinii pneumonia) with reasonable precision, to compare those rates to the background rates among controls, and to provide information about rates in the major transmission categories. The sample is also adequate to estimate and compare the lung function parameters, in terms of DLCO, for Groups A, B, and C and the major transmission categories. In addition, the design will permit adequate comparison of long term prognosis (i.e. mortality) between those intensively studied and those studied in a routine manner. Details of the precision calculations for the above-mentioned parameters are given in Appendix 3.

7.1.5 Recruitment strategies

Study subjects will be recruited from various sources, depending on the Clinical Center and the transmission category to be recruited. Based on the potential sources as delineated below, flyers, brochures, posters, and contact with study personnel will publicize the program. Professional staff at potential reference sources will be briefed about the program and requested to provide information to their clients. Publicity at the Clinical Centers will encourage professional staff to bring potential recruits to the attention of the investigators for inclusion in the cohort. Freestanding clinics or drug treatment programs will be approached by the investigators to ensure that their staff are aware of the project. Other referrals of potential subjects will come from advertisements and press coverage of the activities under the contract. Recruitment strategies for each center are detailed in Appendix 4.

The following is a composite listing of the sources of subjects compiled from the Clinical Centers.

Existing hospital clinics, services and programs: Sexually Transmitted Disease Clinic, Tuberculosis or Chest Clinic, Infectious Diseases Clinic, Pediatric Clinic, AIDS Clinic.

Hospital Consultation Services: Pulmonary Disease Service, Infectious Disease Service.

Existing cohorts: ATEU, CSG, MACS, other established cohorts (having the advantage of demonstrated motivation and commitment already generated by the subject).

Gay community events: Various events may be held by gay men's health associations and similar groups. Support is often requested from local agencies and personnel can be assigned to participate in the event and to convey information concerning the study.

HIV testing sites: Centers that provide voluntary anonymous testing for HIV antibody.

The private practices of physicians who see large numbers of HIV infected persons.

Methadone Treatment Programs and other drug programs (advantage in commitment of subjects to continued care in participation treatment program.)

Individuals responding to word of mouth or media-generated publicity about the project (advantage of subject generated interest in the program).

7.1.6 Enrollment

Potential subjects will be approached and introduced to the study either at the Clinical Center or at the source of referral by one of the investigators and/or program coordinator. After providing a thorough description of the study and obtaining informed consent, an initial interview will be obtained by the investigator and/or coordinator. A physical examination, and initial laboratory examinations (chest film, blood studies, pulmonary function tests and sputum induction) will be performed at the Clinical Centers. A preliminary determination of the subject's category may be made at the initial visit, however, random assignment to the routine (A1,B1) or intensive (A2,B2) follow-up groups will be provided by the Coordinating Center after CD-4 counts are known. The subject will be advised of his/her schedule of visits after the subgroup has been determined.

Subjects who, during the first 12 months after their enrollment, do not appear for evaluation in spite of at least three telephone or mail reminders during a three month period will be replaced by new enrollees. For any subject who does not return for scheduled evaluations, efforts will be made to ascertain his/her status at each of the originally scheduled intervals so long as he/she is not confirmed to be dead.

At the time study enrollment is being considered if the subject agrees the subject's care provider should be contacted, informed of the study, and his/her cooperation sought to ensure that all pulmonary diagnostic evaluations are performed in the Clinical Center.

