Group B subjects, as indicated by their having clinical or laboratory findings indicative of more severe immunosuppression (Table 2), will be at greater risk of developing HIV-associated, often AIDS-defining, lung diseases. It is anticipated that studies of individuals in Group B will serve to determine the natural history of the AIDS-defining processes and to describe the diagnostic features of second and subsequent episodes of P. carinii pneumonia. Because it is estimated (from the data of Moss et al) that approximately 5% of Group A and 20% of Group B patients will develop an AIDS-defining condition each year, in most instances P. carinii pneumonia, a specific group of subjects with existing AIDS will not be recruited.

Inclusion of an HIV-seronegative control group will be necessary to determine if diseases and abnormalities in pulmonary function that are anticipated in Groups A and B are related to the HIV infection or may be caused by lifestyle or other factors independent of HIV infection. Group C will be composed of homosexual/bisexual men and intravenous drug users and will be matched by age, race, and sex with Groups A and B. Homogeneity of transmission group distribution and matching characteristics between Group C and Groups A and B will be continuously monitored by the Coordinating Center with appropriate feedback to the Clinical Centers.

To determine the feasibility and impact of early diagnosis of P. carinii pneumonia subjects in Groups A and B will be assigned at random to equal size groups for either "intensive" (3 month intervals) or "routine" (12 month intervals) testing. Figure 1 describes the group assignments and follow-up intervals.

Figure 1
Group Assignments and Follow-up

(1) Intensive evaluation with history, physical examination and testing every 3 months.

(2) Routine evaluation with history and physical examination every six months and testing every 12 months. (See Table 6 for list of tests.)

Definition of Study Groups

- Group A: HIV seropositive. No symptoms or findings attributable to HIV. CD-4 cells \geq 400 per microliter.
- Group B: HIV seropositive. Either clinical manifestations attributable to HIV within the past 6 months (thrush, hairy leukoplakia, fever $>38^{\circ}$ C persisting > 2 weeks, involuntary weight loss $> 10\%$ of baseline, or diarrhea persisting >1 month) or CD-4 cells < 400 /microliter or both.
- Group C: HIV seronegative homosexual/bisexual men or intravenous drug users.

6. Anticipated Problems

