table analyses of 2 or higher dimensions will be constructed to assess statistically whether or not the different pulmonary diseases tend to occur together or whether they are basically independent. Chi-square tests for association will be appropriate in this situation. Simple adjustment for single confounding variables may be made by Mantel-Haenzel methods and more complicated adjustments will be done by loglinear modelling.

Question 12 is, "Does diagnosis of P. carinii pneumonia by intensive screening decrease both short-and long-term mortality?" All seropositive patients will be included in this analysis and the major comparison of interest will be the intensively screened patients versus those who have been randomized to routine evaluations. Since this is a randomized substudy, there is much less concern about selection bias than for the other questions of interest which involved nonequivalent groups. In this case the principal predictive variable of interest is intensive or routine screening and the outcome is short and long term mortality. Variables confounding the interpretation of the analysis include various forms of treatment which patient may be on. To explore question 12, Kaplan Meier survival curves (or Cox regression if covariables must be dealt with) will be computed and statistically compared. In the calculation of the curves it will be important to take the origins of the survival curve as the time of randomization in order to avoid length biased sampling. Additionally, based on back extrapolation of the slope of decline of CD-4 cell counts the approximate time of HIV infection can be estimated and used as the starting point for the curves.

If the answer to question 12 is "No", one may well wish to investigate the reasons for the lack of impact of the intensive effort. A logical inquiry in this regard is whether or not the lead time between onset of preclinical disease and symptoms is sufficient to permit a significant alteration of the disease process. In this regard, extensions to methodology of Zelen and Feinleib, [Biometrika, 1969, pp.601-614] may be useful in estimating the lead time from incidence and prevalence data from the intensive and routine study arms.

10. Quality Control

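### Vital status of non-attenders is sought every 3 months in the intensive arm and every 6 months in the routine arm, so deaths among them can be found more completely in one randomised arm than the other; the likely effect is small.

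*Protocol*

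**What the plan says.** Section 7.1.6 (Enrollment) sets the tracing rule. For any subject who does not return, "efforts will be made to ascertain his/her status at each of the originally scheduled intervals so long as he/she is not confirmed to be dead".

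The intervals differ by randomised arm. In section 5, subjects are allocated 1:1: "subjects in Groups A and B will be assigned at random to equal size groups". The notes to Figure 1 give the two schedules: "Intensive evaluation with history, physical examination and testing every 3 months" and "Routine evaluation with history and physical examination every six months and testing every 12 months". Table 6 agrees, with history and examination at 3 months in A-2 and B-2 and at 6 months in A-1 and B-1.

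Mortality is the outcome of the randomised comparison (Question 12). Section 9 plans Kaplan-Meier curves, or Cox regression if covariables are needed, and adds: "In the calculation of the curves it will be important to take the origins of the survival curve as the time of randomization".

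On losses, section 7.1.4 says that rates in comparable cohorts "have ranged from approximately 12% to 20" per cent, and it plans on the lower end: "it is anticipated that a total of 1,231 patients will be maintained in the cohort (lost to follow-up rate = 12" per cent). It expects most losses in the first year.

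**The concern.** A comparison of mortality between randomised arms should look for deaths equally hard in both. Here the number of times a lost subject is looked for follows from the allocation. A subject lost at entry is due 12 checks in 36 months in the intensive arm and 6 in the routine arm. If a check can fail, a death has more chances of being found in the intensive arm. Arms with identical true mortality could then show different recorded mortality. If the recorded excess fell in the intensive arm, it would work against the benefit that the substudy looks for. A larger sample would not reduce the difference, and no analysis can recover deaths that were never found.

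**Working it through.** **Inputs.** Three-year mortality is 15% in Group A and 50% in Group B (Appendix 3, note to the mortality tables). Analysed seropositives are 527 + 527 = 1,054 (Table 5B: "Total 527 527 177 1231"), or about 527 per randomised arm. Loss is 12% to 20% (section 7.1.4). Check intervals are 3 and 6 months. The probability q that one check succeeds is not given and is assumed.

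**1. The plan's own precision.** With p = (0.15 + 0.50)/2 = 0.325, the half-width is 1.96 × √(2 × 0.325 × 0.675 / 527) = 0.0566. This agrees with the 6 points in Table 3.8 and Question 12.

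**2. Deaths never found among non-attenders.** A death followed by k checks stays unfound with probability (1 − q)^k. I averaged this over exponential death times matched to 15% and 50% at 36 months, in equal parts, with all non-attenders lost at entry (a severe case). The last two columns multiply the gap by the loss rate.

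| Case | Intensive | Routine | Gap | × 12% | × 20% |
|---|---|---|---|---|---|
| 36 months, check at end, q = 1 | 0.0% | 0.0% | 0.0 | 0.00 | 0.00 |
| 36 months, check at end, q = 0.5 | 2.2% | 4.6% | 2.4 | 0.29 | 0.48 |
| 36 months, no check at end, q = 1 | 2.1% | 4.2% | 2.2 | 0.26 | 0.43 |
| 48 months, no check at end, q = 0.1 | 18.4% | 27.0% | 8.6 | 1.04 | 1.73 |

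If every check succeeds and one falls at the end, nothing is missed and the arms differ only in delay. The last row is an extreme.

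**3. Effect on the estimates.** I simulated 1.5 million subjects with equal true mortality in both arms, follow-up to 36 months with a check at the end, found deaths entered at their true dates, and others censored at the last confirmed-alive contact. Entries are intensive minus routine in percentage points, crude / Kaplan-Meier.

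| q living, q dead | Loss even over 36 months: 12% | 20% | Loss in first year: 12% | 20% |
|---|---|---|---|---|
| 0.5, 0.5 | 0.18 / 0.00 | 0.29 / −0.01 | 0.27 / 0.00 | 0.44 / −0.01 |
| 0.25, 0.25 | 0.29 / 0.00 | 0.49 / 0.00 | 0.55 / 0.00 | 0.89 / −0.01 |
| 0.9, 0.5 | 0.18 / 0.13 | 0.29 / 0.22 | 0.27 / 0.20 | 0.44 / 0.33 |
| 0.9, 0.3 | 0.28 / 0.21 | 0.47 / 0.35 | 0.50 / 0.38 | 0.83 / 0.63 |
| 0.9, 0.1 | 0.24 / 0.16 | 0.40 / 0.27 | 0.50 / 0.35 | 0.82 / 0.59 |

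The first-year columns follow the protocol's expectation about timing and assume that replaced subjects stay in the randomised comparison. Two checks on the range: q = 0.9 for the living and 0.2 for the dead, with 20% lost in the first year, gives slightly more (0.95 / 0.71). If the living are also hard to trace (0.5 against 0.1), Kaplan-Meier shows only 0.02 to 0.25.

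**4. Direction.** The crude difference is never negative, because extra checks can only add found deaths. The Kaplan-Meier difference depends on who is harder to trace. With the living at 0.5 and the dead at 0.9 it reverses, to between −0.13 and −0.33 points.

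**The case against.** A reader might infer that deaths are certainly found more completely in the intensive arm and that the comparison is therefore biased against it. The documents do not support that. The rule repeats the checks until death is confirmed, so a death missed once is sought again. It concerns non-attenders only. The planned analysis is Kaplan-Meier or Cox, in which extra checks also extend the follow-up of living subjects; with equal traceability the two effects cancel. Bias then needs a further condition: that the dead are harder to trace than the living, or that subjects are counted as alive without confirmation. No censoring rule is stated in the protocol, and such rules are commonly left to the SAP. Nor does the effect on Kaplan-Meier have a fixed direction under every assumption (step 4).

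Other routes to news of a death do not depend on the arm: contact with primary physicians, outreach workers and treatment-programme staff (section 7.1.7), and records obtained under a signed release (section 7.2.8). Section 6 also says that failing on this secondary objective would not greatly harm the study.

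All of this stands, and it limits the point to a minor one. Two things remain. The asymmetry is written into a field rule, so it is not a detail merely left for later. And harder tracing of the dead is plausible, since the reminders in section 7.1.6 go by telephone and mail. Appendix 3 also frames the comparison as a difference in mortality proportions, where the crude figures apply if proportions are counted directly.

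**Conclusion.** The point holds in a limited form. The protocol ties the search for deaths among non-attenders to the randomised visit interval, and it states no check that is independent of arm. With imperfect tracing this can produce a spurious mortality difference. At 12% to 20% loss, that difference is about zero in Kaplan-Meier if the living and the dead are equally traceable and censoring is at the last confirmed-alive contact. It is roughly 0.1 to 0.6 points if the dead are harder to trace (0.9 per check for the living; 0.1, 0.3 or 0.5 for the dead), and roughly 0.2 to 0.9 points in crude proportions. In both of these cases it raises apparent mortality in the intensive arm. The success probabilities are assumptions. Against a 6-point half-width the effect is small. A reader might infer that it could hide a real benefit of intensive screening; at this size, that is not shown.

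**What to change.** In section 7.1.6, set the same vital-status dates, counted from randomisation, for non-attenders in both arms, for example every 6 months. Add one vital-status check of all randomised subjects, including those replaced, at a common closing date. Report completeness of vital status by arm. Equal dates and a common closing check remove the scheduled difference in the search; the report shows whether the arms were in fact traced equally well. Clinic visits, tests and treatment do not change. At 6-monthly dates the intensive arm needs fewer tracing attempts, and the cost is a small staff effort at close-out.
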